8.9.3 Additional Efficacy Analyses

Additional analyses will be provided for blood pressure, potassium, spironolactone exposure and quality of life measures as outlined in subsections below.

8.9.3.1 Blood Pressure

Change in AOBP SBP from baseline to Week 12

Treatment groups will be compared for change in AOBP SBP at Week 12 regardless of increase in antihypertensives by using both ANCOVA and repeated measures methods.

An ANCOVA analysis will be carried out using a model that includes baseline AOBP SBP as a continuous covariate and factors for treatment group, baseline serum potassium (K^+ 4.3 to < 4.7 or 4.7 to 5.1 mEq/L), and Type 1 or diabetes mellitus (Yes or No). This analysis will include only ITT subjects who have AOBP SBP (or SMBP if AOBP is missing) at both Baseline and Week 12.

In addition, a repeated measures mixed model analysis will be performed using all ITT subjects who have an AOBP SBP (or SMBP if AOBP is missing) assessment at Baseline and at least one post-baseline assessment at Week 1 or later. The model will include baseline AOBP SBP as a continuous covariate and factors for treatment group, time, baseline serum potassium (K^+ 4.3 to < 4.7 or 4.7 to 5.1 mEq/L), and Type 1 or 2 diabetes mellitus (Yes or No).

AOBP over time

Summaries of AOBP SBP/DBP will be provided at each visit and for change from Baseline, by treatment group. SMBP SBP/DBP may be used for missing AOBP SBP/DBP. Summaries of change at each post-baseline time point will include only subjects who have non-missing values at baseline and at the post-baseline time point of interest.

Mean SBP/DBP and mean change from baseline will be presented graphically.

The change from Baseline in AOBP SBP over time prior to the first date of addition of any new BP medications or increases from any baseline BP medications will also be presented for the subjects who remained on spironolactone through Week 12.

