Since there are substantial differences in international guideline recommendations for target BP in CKD, Rossignol, et al. (Rossignol, 2015) recommend BP levels for defining resistant hypertension that are consistent with those of the general population (ie, office SBP ≥ 140 mmHg or diastolic blood pressure [DBP] ≥ 90 mmHg). Out of office blood pressure measurements have been shown to be more accurate compared with office BP measurements and can exclude white coat hypertension and masked hypertension, both common in patients with CKD. However, more recently, data suggest that automated office BP (AOBP) using an automatic oscillometric monitoring device without study staff present may have less variability; therefore, AOBP measurements will be used in this study for subject selection, treatment decisions, and the primary evaluation of BP effects, and target blood pressure for these patients will be 135/85 mmHg. Home blood pressure (HBP) measurements and subject-measured blood pressure (SMBP) performed at the study site by the patient using the HBP monitor will also be performed. Home blood pressure measurements may also improve adherence to medications by increasing patient involvement (Wolley, 2016).

In this study, the BP comparison of greatest interest will be the between group difference in change from baseline blood pressure which theoretically should reflect the difference in proportion of subjects remaining on spironolactone at Week 12. It is anticipated that a larger proportion of subjects in the placebo plus spironolactone group will meet spironolactone discontinuation thresholds for potassium during the treatment period. To insure the safety of these subjects without confounding the between group comparisons unduly, subjects randomized to the study will be limited to those with systolic AOBP from 135 to < 160 mmHg, who are less likely to require urgent treatment of hypertension should spironolactone be discontinued. All subjects who experience persistent systolic BP of 165 mmHg or greater may be treated with additional antihypertensive therapy chosen by the investigator.

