9.6 Efficacy Analyses

9.6.1 *Primary Efficacy*

The proportion of subjects remaining on spironolactone at Week 12 will be compared between treatment groups (spironolactone/patiromer versus spironolactone/placebo) using the Cochran-Mantel-Haenszel test, stratified by baseline potassium category (4.3 to < 4.7 mEq/L or 4.7 to 5.1 mEq/L). Additionally, a sensitivity analysis will include stratification by study site (small sites will be pooled).

The primary efficacy analysis will be performed using the ITT Population.

Subjects who terminate from the study early or discontinue study spironolactone early, for any reason, will be considered as not having remained on spironolactone.

9.6.2 *Secondary Efficacy*

The secondary efficacy variable for this study is change from Baseline in AOBP SBP at Week 12 or last available assessment prior to addition of any new BP medications or changes to any baseline BP medications.

The secondary efficacy endpoint will be analyzed using an analysis of covariance (ANCOVA) model, with baseline AOBP SBP as a covariate and baseline serum potassium as a categorical factor (K^+ 4.3 – < 4.7 or 4.7 – 5.1 mEq/L). The analysis will use the ITT Population.

9.6.3 *Other Endpoints*

Additional end-points will be compared between treatment groups including (please refer to the statistical analysis plan for further information):

- Change in AOBP SBP from Baseline to Week 12
- Potassium levels over time (measured both centrally and locally)

- Proportion of subjects with serum $K^+ \geq 5.5$ mEq/L
- Average daily dose and cumulative dose of spironolactone
- Time to discontinuation of spironolactone
- Change from baseline to Week 12 in albuminuria (ACR)
- EQ-5D-5L questionnaire results at Baseline and at Week 12/ET

Change in AOBP at Week 12 will be analyzed with an ANCOVA model using the BPA Population. Additionally, change at Week 12 will be analyzed using a repeated measures mixed model that will include all ITT subjects with at least one measurement of AOBP SBP at Week 1 or later. Models will include baseline AOBP SBP as a covariate and baseline serum potassium as a categorical factor (K^+ 4.3 – < 4.7 or 4.7 – 5.1 mEq/L).

Potassium levels will be summarized for local and central values at each time point. Counts (%) of subjects who have experienced no potassium measurement ≥ 5.5 mEq/L will be presented at each time point.

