Appendix C: Spironolactone Dosing

Spironolactone will be initiated for all randomized subjects on Day 1, at a dose of 25 mg taken orally QD. At Week 3, for subjects with AOBP SBP \geq 120 mmHg and K^+ \leq 5.1 mEq/L, spironolactone will be increased to 50 mg QD. For subjects with K^+ $>$ 5.1 mEq/L, 25 mg daily dose of spironolactone will be continued until the first subsequent visit when K^+ is \leq 5.1 mEq/L (and AOBP SBP \geq 120 mmHg), at which time spironolactone will be increased to 50 mg QD.

Subjects with AOBP SBP $<$ 120 mmHg at the Week 3 Visit will continue their 25 mg daily dose, unless symptoms of hypotension are present in which case the spironolactone dose may be reduced to 25 mg every other day or discontinued altogether, at the discretion of the Investigator. Spironolactone may be reduced or discontinued for AOBP SBP $<$ 100 mmHg. If spironolactone is discontinued, patiromer/placebo must be discontinued at the same time. These subjects will remain in the study and be followed per protocol. Note: At any study visit spironolactone dose may be reduced or discontinued for AOBP SBP $<$ 120 mmHg with symptoms of hypotension, or for AOBP SBP $<$ 100 mmHg at the direction of the investigator. Figure 3 describes spironolactone dosing adjustments by Visit and level of SBP (AOBP).

Figure 3: Spironolactone Titration

AOBP = automated office blood pressure; K⁺ = potassium; PI = Investigator; QD = once daily; QOD = once every other day; SBP = systolic blood pressure.

^a If spironolactone is discontinued, patiromer/placebo must be discontinued at the same time. These subjects will remain in the study and be followed per protocol. After study drug discontinuation, the treatment of hypertension should proceed in accordance with the standard of care for BP management and the Investigator’s judgment.

NOTE: At Week 12 all subjects will discontinue all study medications (spironolactone and patiromer/placebo).

Changes in Spironolactone Dosing Based on eGFR

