2.2 Study Design

This study is a randomized, double-blind, placebo-controlled, parallel group study of patiromer or placebo treatment (patiromer/placebo) in conjunction with spironolactone in subjects with resistant hypertension and CKD. Approximately 290 subjects will be randomized.

Screening for this study includes 4 visits and lasts up to 4 weeks. Subjects who meet all eligibility criteria are randomized to receive either spironolactone and patiromer or spironolactone and placebo. The active treatment period runs for 12 weeks. A follow-up visit is scheduled 2 weeks after completion of the Week 12 or Early Termination (ET) Visit.

Study periods are as follows:

- Screening Period (4 Visits)
Screening Visit 1 (S1), Screening Visit 2 (S2), Screening Visit 3 (S3) and Screening Visit 4 (S4) occur one week apart (at least 4 days but no more than 10 days). If the subject meets all eligibility criteria at the final screening visit (S4), the visit becomes the Randomization/Baseline Visit.
- Double-Blind Treatment/Observation Period (12 weeks)
At the Randomization/Baseline Visit, each subject is randomized to either spironolactone + patiromer or spironolactone + placebo, and is instructed to begin study drug on the following day, which then becomes Day 1 of the study.

The Double-Blind Treatment/Observation Period consists of 8 scheduled visits at Weeks 1, 2, 3, 4, 6, 8, 10, and 12. The intent is to observe all subjects for the entire 12 weeks of this period, whether or not they have discontinued study drug.

- Follow-up Period

[figure not shown]
Two weeks after the subject has completed either the Week 12 Visit or ET Visit, the subject returns for a Follow-up (FU) Visit.

The Schedule of Events for this study is presented in Appendix A.

The initial dose of spironolactone will be 25 mg QD for all subjects, and the initial dose of patiromer/placebo will be 2 packets QD. If a subject's blood pressure and potassium assessments allow, the dose of spironolactone will be increased to 50 mg QD at Week 3. Detailed titration rules for spironolactone and patiromer/placebo are specified in the protocol in Appendix B (patiromer/placebo) and Appendix C (spironolactone).

The overall design of the study is presented schematically below in Figure 1.

Figure 1. Study Schema

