8.9.2 Secondary Efficacy Analysis

The secondary efficacy endpoint is change from Baseline in AOBP SBP at Week 12 or last available AOBP SBP on or prior to the first date of addition of any new BP medications or increases from any baseline BP medications.

Baseline AOBP is defined as the latest available AOBP on or before the date of first dose date.

Changes/additions to baseline BP medications are recorded on the Antihypertensive Medications eCRF. The earliest date of any recorded increase/addition will be compared to the date of the Week 12 AOBP, and the rules below will be applied. Note that only dates of BP medication increases/additions with start date on or before the upper limit of the Week 12 window will be considered.

- If the earliest date of BP medication increase/addition is on or after the date of the Week 12 AOBP, or there is no record of any increase/addition, the Week 12 AOBP SBP will be used for analysis.
- If the earliest date of BP medication increase/addition is prior to the Week 12 AOBP, or when the Week 12 visit should have occurred if there is no Week 12 AOBP, then the AOBP on or before and closest to the earliest date of change will be used for analysis.
- If a subject has no Week 12 AOBP and no record of any BP medication changes/additions, the subject will not be included in this analysis.

In above rules, the SMBP, if available, may be used in place of a missing AOBP at the same visit.

The secondary efficacy endpoint will be analyzed using an analysis of covariance (ANCOVA) model, with baseline AOBP SBP as a continuous covariate and factors for treatment group, baseline serum potassium (K^+ 4.3 – < 4.7 or 4.7 – 5.1 mEq/L), and Type 1 or 2 diabetes mellitus (Yes or No).

The analysis will be performed using the ITT and PP Populations. A sensitivity analysis will be performed using the last observation carried forward, when a subject has no Week 12 AOBP and no record of any BP medication changes/additions.

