8.9.4 Subgroups

The primary and secondary analyses will be performed for the following subgroups:

- Sex (male versus female)
- Age (< 65 versus \geq 65 years)
- Type 1 or Type 2 diabetes mellitus (presence versus absence at baseline)
- Baseline potassium category (4.3 to < 4.7 mEq/L versus 4.7 to 5.1 mEq/L) from central lab
- Region (Group A versus Group B)
- History of heart failure (presence versus absence at baseline)
- Baseline eGFR (< 30 versus \geq 30 mL/min/1.73 m²)

The test for interaction between treatment and a subgroup will be performed.

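### The mixed model meant to compare groups at Week 12 has no treatment-by-time term, so as written it estimates an average effect over eight visits and understates a Week 12 difference that builds over time

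*SAP*

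**What the plan says.** SAP 8.9.3.1 states the target for this endpoint: "Treatment groups will be compared for change in AOBP SBP at Week 12 regardless of increase in antihypertensives", using both ANCOVA and repeated-measures methods. Protocol 9.6.3 has the same target: "change at Week 12 will be analyzed using a repeated measures mixed model".

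For the mixed model the SAP then lists the terms: "The model will include baseline AOBP SBP as a continuous covariate and factors for treatment group, time, baseline serum potassium", and finally diabetes status. The analysis takes all ITT subjects with a baseline value and at least one value from Week 1 onward. The double-blind period "consists of 8 scheduled visits at Weeks 1, 2, 3, 4, 6, 8, 10, and 12" (SAP 2.2), so eight post-baseline visits enter the model.

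Neither document names a treatment-by-time interaction, a Week 12 contrast or a within-subject covariance structure. The one interaction named in the SAP concerns subgroups (8.9.4): "The test for interaction between treatment and a subgroup will be performed".

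**The concern.** With treatment and time as main effects only, the model has one treatment coefficient for all visits. That coefficient equals the Week 12 difference when the difference is constant from Week 1, and otherwise only by coincidence.

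The documents give reasons to expect a difference that grows:

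- Protocol 1.2 expects the between-group BP difference, which "theoretically should reflect the difference in proportion of subjects remaining on spironolactone at Week 12". Both arms start the same spironolactone dose on Day 1, and discontinuations accumulate afterwards.
- From Week 3 the dose step depends on potassium. For subjects above the potassium limit, the "25 mg daily dose of spironolactone will be continued until the first subsequent visit when" potassium is back within it (Protocol Appendix C). The arms can therefore separate in dose without any discontinuation.
- Protocol 1.1.2 puts the steady-state effect of spironolactone after 6 weeks of treatment.

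Two things are at stake. First, a result labelled as a Week 12 comparison could be well short of the Week 12 effect. Second, within this endpoint the mixed model is the only analysis that keeps subjects without Week 12 data, because the ANCOVA beside it requires a value at both Baseline and Week 12. It is the natural check on missing data. As listed, it can disagree with the ANCOVA through model form alone, and a reader could take that for an effect of dropout.

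**Working it through.** The plan states no figure for this model, so there is nothing of its own to reproduce. The check asks what the listed model estimates.

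**Inputs.** Visits at Weeks 1, 2, 3, 4, 6, 8, 10 and 12 (SAP 2.2); model terms from SAP 8.9.3.1. The within-subject covariance and the time course of the effect are not in the documents. They are assumed and varied.

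**Formula.** Let d be the vector of true treatment differences at the eight visits and S the within-subject covariance. With complete data, categorical time and no treatment-by-time term, the treatment coefficient estimates a'd, where a = S⁻¹1 / (1'S⁻¹1). The fraction of the Week 12 effect recovered is a'd / d(12).

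**Weights**

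| Covariance | Week 1 | Weeks 1–4 | Week 12 |
|---|---|---|---|
| Compound symmetry | 0.125 | 0.500 | 0.125 |
| Autoregressive, 0.7 per 2 weeks | 0.276 | 0.433 | 0.298 |
| Autoregressive, 0.85 per 2 weeks | 0.360 | 0.458 | 0.374 |
| Half compound symmetry (0.6), half autoregressive (0.7) | 0.184 | 0.446 | 0.229 |

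Weeks 1 to 4 carry 43% to 50% of the weight, and Week 12 carries 12.5% to 37%.

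**Worked case by hand.** Under compound symmetry every visit has weight 1/8, whatever the correlation. For a linear build, d(t) = t/12, and the fraction is (1+2+3+4+6+8+10+12)/(8 × 12) = 46/96 = 0.479.

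**Fraction of the Week 12 effect, range over the four covariances**

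| Time course of the difference | Fraction |
|---|---|
| None to Week 3, then linear | 0.35–0.47 |
| Linear from Week 0 | 0.48–0.54 |
| Exponential discontinuation to 60% v 80% retention | 0.54–0.58 |
| Step at Week 4 | 0.58–0.63 |
| Plateau by Week 6 | 0.65–0.71 |
| Front-loaded discontinuation (Weibull shape 0.5) | 0.71–0.74 |
| Plateau by Week 4 | 0.71–0.81 |
| Constant from Week 1 | 1.00 |
| Peak at Week 6, halved by Week 12 | 0.88–1.17 |
| Peak at Week 4, halved by Week 12 | 0.96–1.31 |

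**Simulation check.** Assumed: 140 per arm, SD 12 mmHg, compound symmetry with correlation 0.5, no dropout, and a linear build to −4.0 mmHg at Week 12; 60 replicates.

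| Analysis | Mean estimate (mmHg) | Mean SE |
|---|---|---|
| Model as listed | −1.95 | 1.07 |
| Treatment-by-visit added, Week 12 contrast | −4.07 | 1.43 |
| Week 12 ANCOVA | −4.06 | 1.44 |

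The Monte Carlo SE of the mean estimate is 0.14 for the listed model and 0.21 for the other two. The listed model recovers 1.95/4.0 = 0.49, in line with the algebra.

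**Cost in precision.** With equal variances at all visits, the Week 12 contrast has a CI wider than that of the all-visit average by √(1'S⁻¹1) with unit variance: 1.33 for compound symmetry (0.5), 1.40 and 1.20 for the two autoregressive cases, and 1.31 for the mixture. The simulation gives 1.43/1.07 = 1.34.

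**The case against.** The strongest reply is that this is an incomplete sentence and not a wrong model. The stated target is Week 12, a statement of what a model will include need not be exhaustive, and Protocol 9.6.3 omits even treatment and time from its list. An analyst could add visit-specific differences without contradicting the text. That is possible, but the SAP is where the detail is meant to be settled and it takes precedence over the protocol. A programmer following its list would fit the main-effects model. An interaction, covariance and contrast added later would not be prespecified. The subgroup sentence in 8.9.4 is weak evidence either way, because it writes out no model terms.

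The second reply concerns direction. This analysis counts BP regardless of added antihypertensives. If placebo subjects stop spironolactone more often and are then given other BP drugs, a late difference could narrow. The listed model can then overstate the Week 12 effect, as the fading rows above show. This stands: understatement depends on the difference building. It is a further reason not to report the average as a Week 12 result.

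Third, nothing in the documents ranks gradual build-up above early build-up, so one half is not a settled figure. That stands too, and the range should be quoted.

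Fourth, the consequence is limited. The same SAP section plans summaries and graphs of SBP by visit and treatment group, which would show a growing or fading difference. They are descriptive and use observed cases only, so they soften the risk without supplying the missing contrast.

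**Conclusion.** The concern holds. As listed, the mixed model does not estimate the Week 12 difference that the SAP and protocol name as its target. If the difference builds over time, the model recovers roughly 0.35 to 0.8 of it, and about 0.5 if the build-up is gradual. If the difference is constant there is no dilution. If it fades, the result can lie on either side of the Week 12 effect (0.88 to 1.31 in the patterns tried). These fractions assume complete data and the covariances and time courses shown. The model algebra does not depend on those choices.

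The reach is modest. This is one of two analyses of an 'other' endpoint. The primary CMH test, the sample size and the Week 12 ANCOVA do not change. The secondary ANCOVA has its own missing-data provision ("A sensitivity analysis will be performed using the last observation carried forward, when a subject has no Week 12 AOBP" and no recorded BP medication change, SAP 8.9.2) and is also untouched. The correction should be made, but no main conclusion of the trial rests on it.

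**What to change.** In SAP 8.9.3.1:

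1. State that visit is categorical. Listing time among the factors already suggests this.
2. Add the treatment-by-visit interaction.
3. Name the within-subject covariance structure.
4. Define the reported estimate as the Week 12 treatment contrast with its 95% CI.

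A baseline-by-visit term and an unstructured covariance are reasonable but optional.

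The cost is SAP wording, with no change to data collection, sample size or any clinical rule. The interval will be about 1.2 to 1.4 times as wide as that of the all-visit average under the assumptions above. The narrower interval belongs to a different quantity, so no precision about Week 12 is lost. If an average over visits is also wanted, it can be kept as a separately labelled estimate.

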8.9.3.2 Potassium

Central serum potassium levels and change from Baseline will be summarized, by treatment group, at each scheduled visit.

Central serum potassium over time will be presented graphically.

Number and percentage of subjects who have experienced no $K^+ \geq 5.5$ mEq/L will be presented by visit. All central laboratory potassium values will be used for this analysis.

Local laboratory potassium values from serum samples will be included in listings.

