9.3 General Considerations

Local potassium values will be used for randomization/stratification, titration of the blinded study medication (patiromer/placebo), and discontinuation of spironolactone. Central serum potassium values will be used for the analysis of change in potassium over time.

Subjects will be screened for eligibility at Screening Visits 1 – 4 (S1, S2, S3, and S4). If a subject meets all eligibility criteria at Visits S1 – S4, the subject will be randomized at the S4/Baseline (Day 0) Visit (Appendix A). The subject will take his or her first dose of spironolactone and first dose of blinded study medication (patiromer/placebo) on the day after this visit (Day 1).

Tables will be presented by treatment group and overall, unless otherwise specified in the SAP.

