6.1.3 Other Efficacy Endpoints

The following other efficacy endpoints were specified by the protocol:

- Change in AOBP SBP from baseline to Week 12
- Potassium levels over time (measured both centrally and locally)
- Proportion of subjects with serum $K^+ \geq 5.5$ mEq/L
- Average daily dose and cumulative dose of spironolactone
- Time to discontinuation of spironolactone
- Change in albuminuria (urine albumin to creatinine ratio [ACR]) from baseline to Week 12
- EQ-5D-5L questionnaire results at Baseline and Week 12/ET

In addition to the endpoints specified in the protocol, the following additional endpoints will be examined:

- Change in AOBP SBP from baseline to Week 12 in the subgroup of patients remaining on spironolactone at Week 12
- Change in AOBP SBP/DBP over time

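### SAP 8.9.3.2 counts K+ ≥ 5.5 mEq/L from central values only, lists local values, and plans no between-arm estimate, although its endpoint list names both laboratories and local values drive stopping

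*SAP*

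**What the plan says.** SAP 6.1.3 lists "Potassium levels over time (measured both centrally and locally" among the efficacy endpoints, together with the proportion of subjects whose serum K+ reaches 5.5 mEq/L.

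SAP 8.9.3.2 is the section that should deliver both. It summarizes and plots central potassium. For the threshold it presents "Number and percentage of subjects who have experienced no" value at or above 5.5, by visit, and adds "All central laboratory potassium values will be used for this analysis". On the other laboratory it says "Local laboratory potassium values from serum samples will be included in listings".

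Protocol 9.6.3 introduces the same endpoints with "Additional end-points will be compared between treatment groups including" and plans visit summaries for local as well as central potassium. Protocol 9.3 divides the roles of the laboratories: "Local potassium values will be used for randomization/stratification, titration of the blinded study medication (patiromer/placebo), and discontinuation of spironolactone", and then "Central serum potassium values will be used for the analysis of change in potassium over time".

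Both Protocol 9 and SAP 1 give the SAP precedence where the two differ.

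**The concern.** The trial's stated aim is longer use of spironolactone because hyperkalemia is prevented. The rationale in Protocol 1.2 leans on a between-arm contrast of this kind: in a subgroup of an earlier heart failure study, 56% on placebo against 0% on patiromer exceeded 5.5 mEq/L. The proportion reaching 5.5 is therefore the endpoint that links the drug to the primary result.

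As planned, that link is measured in a different laboratory from the one that triggers stopping, and no estimate of the difference between arms accompanies it. A report could then show subjects stopped for high potassium who appear in the efficacy table as never having had it. The local summary that would explain the discrepancy would exist only as a listing.

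**Working it through.** The plan states no figure for this endpoint. Its one design figure, 280 subjects for the primary comparison, does not enter here. The check is mainly one of text.

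**1. Endpoint list against analysis section.**
- Local potassium over time: an endpoint in SAP 6.1.3, to be summarized in Protocol 9.6.3, listed only in SAP 8.9.3.2.
- K+ ≥ 5.5: Protocol 9.6.3 does not restrict the count to one laboratory, and Protocol 9.3 assigns central values to change over time. SAP 8.9.3.2 restricts the count to central.
- Comparison: SAP 8.9.3.3, the next subsection, names ANCOVA and a log-rank test for spironolactone exposure. SAP 8.9.3.2 names nothing comparable. SAP 8.10.4.1 tabulates the incidence of ≥ 5.5 by arm, descriptively.

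**2. Missing central values.** Protocol 7.1.1 says that a sample found hemolyzed at the central laboratory is not redrawn, and that the SAP covers the missing value. Protocol 9.7 allows a same-day local value in its place and leaves the details to the SAP. SAP 7 covers dropouts, missing AOBP, adverse-event fields and dates. It has no potassium rule, and SAP 7.4 rules out imputing other missing safety data.

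**3. One subject traced through.** A subject stops after a local value of 5.5 or more. If all central values are below 5.5, or the central value at that visit is lost and no other reaches 5.5, the central data hold no event. The subject falls in the no-event group, and no SAP rule prevents this.

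**4. Can the size be computed?** Not from the documents. As an illustration, assume central = local + bias + normal error. Then for one paired sample P(central < 5.5 | local = x) = Φ((5.5 − x − bias)/SD). With bias 0 and SD 0.2:
- x = 5.5: Φ(0) = 50%
- x = 5.6: Φ(−0.5) = 31%
- x = 6.0: Φ(−2.5) = 0.6%

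Over SD 0.1 to 0.3 and bias −0.2 to 0 mEq/L the ranges are 50 to 98%, 16 to 84% and 0 to 16%. The answer depends almost wholly on the assumptions.

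**5. Can the direction be fixed?** No; two assumed cases point opposite ways.
- Misses only: local incidence 50% against 30%, with central missing 10%, 20% or 30% of events. The counted difference is 45 − 27 = 18, 40 − 24 = 16 or 35 − 21 = 14 points instead of 20.
- Symmetric error at a single visit: local mean 5.0, SD 0.5, error SD 0.2. The local share is 1 − Φ(0.5/0.5) = 15.9%. The central SD is √(0.25 + 0.04) = 0.539, so the central share is 1 − Φ(0.5/0.539) = 17.7%. Central-only positives more than offset the misses.

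**The case against.** Central values are a reasonable choice for analysis: one laboratory with a hemolysis check, against local laboratories at about 60 sites. This stands, and central can remain the main source. It does not explain why a listed local endpoint has no summary.

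The Protocol's promise to compare is loose. The same lead-in covers EQ-5D-5L, which is only summarized; for K+ ≥ 5.5 the Protocol itself specifies counts and percentages, and it defers to the SAP. This also stands: the missing test alone breaks no firm commitment. The missing local summary does.

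Hyperkalemia that leads to stopping is not lost. An out-of-range result that leads to discontinuation of patiromer is an adverse event (Protocol 8.1). SAP 8.10.1 tabulates events leading to discontinuation by arm and by study drug, reasons for discontinuing are a safety endpoint (SAP 6.2), and time to stopping spironolactone is compared by log-rank. A reader might infer that the mechanism is never compared between arms. With these tables and the incidence in SAP 8.10.4.1, that goes too far; what is missing is an inferential estimate for the named endpoint.

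Misclassification is possible, not certain. Central samples are drawn at every visit, including unscheduled ones, and all of them count. A local value of 5.5 may lead first to packet escalation, so some stopped subjects will have several central draws.

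Finally, deleting the reference to local values from SAP 6.1.3 would restore consistency more cheaply. It would also discard the values on which stopping was decided.

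**Conclusion.** SAP 8.9.3.2 does not carry out SAP 6.1.3 or the local summary planned in Protocol 9.6.3. It gives a named efficacy endpoint no between-arm estimate, and it leaves out the missing-value rule that the Protocol assigns to the SAP. These points rest on the text alone. The affected endpoint is a supportive one; the primary analysis does not use it.

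Three stronger readings are not supported.
- A reader might take 25 to 37% as the share of stopped subjects missed: Φ(−0.1/0.15) = 25% and Φ(−0.1/0.30) = 37%. That holds for one paired sample at a local value of exactly 5.6, with no bias and assumed SDs.
- A reader might infer net under-counting, larger in the arm with more stops. Step 5 shows that even the sign is open.
- A reader might infer that early leavers count as event-free. SAP 8.9.3.2 gives no denominator, so this is an ambiguity to close.

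**What to change.** Amend SAP 8.9.3.2 before unblinding:
- Summarize local potassium, and its change from baseline, by visit and arm as for central.
- Report the proportion with any K+ ≥ 5.5 mEq/L through Week 12, once by central and once by local values.
- Compare arms with a CMH test stratified by the two randomization factors, plus a risk difference with 95% CI, and label this supportive.
- State the denominator for subjects who leave early, or use Kaplan-Meier time to first K+ ≥ 5.5 with those subjects censored.
- Add the rule for using a same-day local value when the central value is missing, as Protocol 9.7 foresees, and make SAP 7.4 consistent with it.

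No new data are needed, since local values are already collected for the planned listings. The cost is SAP wording, a few tables and a few more unranked comparisons, which the supportive label keeps in proportion.
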